**Additional RFS rules related to death will be evaluated in sensitivity analyses as follows.**

- **RFS Sensitivity # 2:** The primary analysis of RFS will be repeated with the consideration that in the absence of prior documented recurrence, death beyond 90 days after the last valid tumor evaluation or randomization date (whichever is later) will not be considered an event, and instead will result in a censored RFS time.
- **RFS Sensitivity # 3:** The primary analysis of RFS will be repeated with the consideration that in the absence of prior documented recurrence, deaths not determined to be related to melanoma will not be considered an event. Deaths will be will considered as related to melanoma if the death reason is disease progression or unknown.

**RFS sensitivity analysis # 2 and/or # 3** will be conducted if RFS is revised for more than 10% of subjects in either arm due to revised specification, or if the absolute between-arm frequency difference is greater than 5%.

#### **4.1.2 Secondary Endpoint**

##### **4.1.2.1 Efficacy Endpoints**

##### **4.1.2.1.1 Tumor Response (Arm 1 Only)**

The overall tumor response is evaluated up to the earlier of surgical resection or subsequent anti-cancer therapy. Lesion-level response is evaluated up to the earliest event of start of subsequent anti-cancer therapy, merge with another lesion, or resection. Subject-level response is evaluated up to the earliest event of start of subsequent anti-cancer therapy or a partial or complete lesion resection.

Following endpoints will be analyzed for tumor response analysis,

- The overall tumor response is per the modified WHO criteria of tumor.
- Tumor response in injected/uninjected lesion(s)
  - The subject-level injected and uninjected responses will be based on the tumor burden of only injected index lesions including injected new measurable lesions, or the tumor burden of only uninjected index lesions including uninjected new measurable lesions, respectively.
  - The lesion-level injected and uninjected response will evaluate the change of the area of each individual lesion.
- Similar to tumor response in injected/uninjected lesions, lesion-level and subject-level response may also be conducted for lesion subtypes, eg, cutaneous / subcutaneous, nodal.

For the subject-level tumor response by tumor burden type (injected, uninjected lesions), a response is achieved if the percentage of the specific tumor burden type reduction from baseline for both baseline and new measurable lesions (if applicable) is at least 50%. Overall tumor burden is calculated at a visit as the sum of tumor areas of all lesions of the same type. The incidence of subject-level tumor response will be reported as the proportion of subjects with an evaluable tumor burden of the corresponding type that achieves a response.

The incidence of lesion-level response will be reported as the proportion of evaluable lesions in response. A lesion is in response if the decrease in tumor area is  $\geq 50\%$ .

All overall tumor burden and lesion response analyses will be based on bi-dimensional lesion measurements reported at a tumor assessment and will not consider injected lesion longest diameters reported at the time of investigational product administration forms.

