- multiple superficial melanoma lesions which in aggregate have a total diameter of ≥ 10 mm

Nonmeasurable Lesions:

All other lesions, including small lesions (longest diameter < 10 mm by CT/MRI/ultrasound for nodal/soft tissue disease [including lymph nodes] or < 10 mm caliper measurement by clinical exam for superficial cutaneous melanoma lesion) and other truly nonmeasurable lesions are considered nonmeasurable and characterized as nonindex lesions. This will include any measurable lesions beyond the maximum number of 10 lesions that were not chosen as index lesions.

Lesions with Prior Local Treatment:

Tumor lesions situated in a previously irradiate area, or an area subject to other loco-regional therapy, are usually not considered measurable unless there has been demonstrated progression in the lesion.

Coalescing or Splitting Lesions:

Coalescing lesions: When two or more lesions merge and at least one is an index lesion, the largest index lesion prior to merging should be measured and reported during the tumor response assessment. All other merged lesions should be reported as 0 mm x 0 mm (for lesions previously reported as Index or New Measurable Lesions) or absent (for lesions previously reported as Non-Index or New Non-Measurable Lesions). If two or more non-index lesions merge, the apparently larger lesion should be reported as present, and smaller lesion(-s) should be reported as absent. The indication that the lesion coalesced with the specified lesion(-s) should be provided for each merged lesion.

Splitting lesions: When an index lesion splits into two or more lesions the largest measurable part of the split lesion will be measured for the current assessment with the indication that the lesion split from the specified lesion, and followed for future assessments. The remaining lesions will be measured as new lesions with an indication that the lesion split from the specified lesion. In this case, appearance of a new lesion from a previous lesion that split will not be considered disease progression solely due to appearance of a new lesion (may be considered disease progression due to > 25% increase in the sum of the products of the perpendicular diameters of all index tumors since baseline, or the unequivocal appearance of a new tumor, other than the product of the split tumor, since the last response assessment time point).

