At each subsequent tumor assessment, the sum of the products of the two largest perpendicular diameters of the index lesions are added together to provide the total tumor burden.

Follow-up “Nonindex Lesions”:

Nonindex disease measurements are not required and these lesions should be followed as “present”, “absent”, or in rare cases “unequivocal progression”.

Follow-up “New Lesions”:

At tumor assessment, if new measurable lesions have appeared they should be added to sum of the products of the two largest perpendicular diameters of the index lesions to provide the total tumor burden. For nonmeasurable new lesion they should be followed as nonindex lesion as “present”, “absent”, or in rare cases “unequivocal progression”. If a new lesion(s) that appears in between scheduled tumor response assessments disappear(s) before the next scheduled assessment, there is no need to include this lesion for tumor response evaluation.

Response Criteria

Evaluation of Objective Response:

The subject response will be assessed based on the response of the index lesions and nonindex lesion, and presence or absence of new lesions. Confirmation of complete or partial response is not required. The overall response is derived from time point response assessments as described in [Table 1](#), [Table 2](#), and [Table 3](#).

Table 1. Definition of Index Lesion Tumor Response Including New Measurable Lesions

Complete Response (CR):	Complete disappearance of all index lesions, including any new measurable tumor lesions which might have appeared.
Partial Response (PR):	Achieving a 50% or greater reduction in the sum of the products of the two largest perpendicular diameters of all index lesions and new measurable lesions, if applicable, at the time of assessment as compared to the sum of the products of the perpendicular diameters of all index lesions at baseline.
Disease Progression (PD):	A > 25% increase in the sum of the products of the perpendicular diameters of all index tumors since baseline, or the unequivocal appearance of a new measurable lesion since the last response assessment time point.
Stable Disease (SD):	Neither sufficient tumor shrinkage of index lesion to qualify for response (PR or CR) nor sufficient tumor increase of index lesion to qualify for PD.
Unable to Evaluate (UE):	Any index lesion present at baseline which was not assessed or was unable to be evaluated leading to an inability to determine the status of that particular tumor for that time point.

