Pathological Complete Response (pCR) is defined as no evidence of viable tumor cells on complete pathological evaluation of the surgical specimen per institutional standards of care. pCR rate is defined as proportion of subjects which achieves a pCR. For each subject, the pCR status (pCR or non-pCR) will be determined based on whether or not viable tumor was detected in the surgical specimen.

- Last Valid Tumor Evaluation

For overall tumor response per modified WHO response criteria the last valid tumor evaluation refers to the last valid tumor response assessment (PR, CR, SD or PD) per investigator. For the subject-level tumor response based on the tumor burden of a subset of lesions (injected, uninjected lesions, or other subtype) or the lesion-level response the last valid tumor evaluation refers to the assessment where the corresponding tumor burden or the corresponding individual tumor area is not missing.

- Baseline Lesion

Lesions measured at the most recent visit on or before receiving the first administration of talimogene laherparepvec (i.e., study day 1) will be flagged as baseline lesions. Baseline lesions must have positive tumor area. Lesions reported in the baseline measurable lesion CRF page but with a tumor area of zero or missing value at the last measurement on or before study day 1 will not be considered baseline lesions.

- New Lesion

New lesions are those that first appear after study day 1 with a positive tumor area or lesions without a positive lesion area in the last assessment on or before study day 1

but a positive lesion area from follow up tumor measurements. Baseline tumor area of a new lesion is obtained from the earliest date with positive bi-dimensional tumor measurements after study day 1. If a new lesion(s) that appears in between scheduled tumor response assessments disappear(s) before the next scheduled assessment, there is no need to include this lesion for tumor response evaluation

- Evaluable Lesion

A baseline or new measurable lesion is defined as evaluable if it has an initial positive area followed by at least 1 assessment with a non-missing area.

- Injected/Uninjected Lesion

Baseline or new lesions that are reported as injected with talimogene laherparepvec at any time during the treatment period are considered injected lesions. Baseline or new lesions that are not reported as injected with talimogene laherparepvec are considered uninjected lesions.

- Baseline Tumor Burden

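### The SAP has no rule for a split lesion and stops at a merge only for lesion-level response, so a change of lesion geometry can be scored as a response, or hide one, in the Arm 1 lesion-level and injected/uninjected analyses

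*SAP*

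**What the plan says.** Protocol Appendix D (Coalescing or Splitting Lesions) fixes how sites record these events. After a merge, "the largest index lesion prior to merging should be measured and reported during the tumor response assessment". For the rest: "All other merged lesions should be reported as 0 mm x 0 mm (for lesions previously reported as Index or New Measurable Lesions"). After an index lesion splits, "the largest measurable part of the split lesion will be measured for the current assessment", and "The remaining lesions will be measured as new lesions with an indication that the lesion split from the specified lesion". Sites therefore record which lesion merged with, or came from, which. For the overall burden, Appendix D also provides: "At tumor assessment, if new measurable lesions have appeared they should be added to sum of the products".

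The SAP then analyses single lesions and separate injected and uninjected burdens. Section 4.1.2.1.1 has two stopping rules. At lesion level: "Lesion-level response is evaluated up to the earliest event of start of subsequent anti-cancer therapy, merge with another lesion, or resection". At subject level: "Subject-level response is evaluated up to the earliest event of start of subsequent anti-cancer therapy or a partial or complete lesion resection". A merge appears only in the first, and a split in neither. At both levels a reduction of at least 50% is a response.

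SAP Section 6 classifies lesions by their own injection record: "Baseline or new lesions that are not reported as injected with talimogene laherparepvec are considered uninjected lesions". Its definition of a new lesion makes no exception for a split fragment. The two SAP sections also disagree on burden: 4.1.2.1.1 counts new measurable lesions along with baseline lesions at subject level, while the Section 6 entry for tumor burden sums baseline lesions alone.

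**The concern.** The Appendix D recording rules work for a total over all lesions, because area lost from one line of the form reappears on another. They do not work for a single lesion or for a burden restricted to one lesion type, because the area can reappear outside the set being analysed. Three cases follow.

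- **Split, lesion level.** The parent's area becomes that of its largest part. If that is at most half the baseline area, the parent is a responder even with almost no tumor loss.
- **Merge across types, subject level.** When an injected and an uninjected lesion merge, the absorbed one is entered as 0 x 0 mm. That is a non-missing area, so the assessment stays evaluable and the burden of that type falls.
- **Split, subject level.** Area leaves the injected burden if the fragment is never reported as injected. Under the Section 6 burden wording it leaves even if the fragment is injected.

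Response in injected and uninjected lesions is a named secondary objective (protocol 1.2). One reading can settle it: before surgery only one post-baseline tumor assessment is normally scheduled, at week 12 or shortly before an early operation (protocol Table 2 and 7.2.2), and Appendix D requires no confirmation of response.

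**Working it through.** The plan states no figure on this point, so there is none to reproduce. All lesion sizes below are assumptions chosen to show the rule at work. The formula is reduction = 1 - (area at visit / baseline area), with area the product of the two diameters, compared with 50%.

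**1. Lesion-level split.** Parent 30 x 20 = 600 mm². Parts 18 x 16 = 288 and 20 x 14 = 280, total 568.
- Whole tumor: 1 - 568/600 = 5.3%.
- Lesion as scored: 1 - 288/600 = 52%, a response.
- General condition: with true shrinkage *s* and a largest part that is a share *f* of what remains, a response is scored when *f*(1 - *s*) ≤ 0.5. With *s* = 0, *f* must be at most 50%; a 60/40 split reads -40% and is no response. With *s* = 20%, *f* ≤ 0.5/0.8 = 62.5% suffices.
- Under SAP Section 6 a new lesion is evaluable only with a later measurement. A fragment first measured at week 12 would usually not enter the lesion denominator, while its parent counts as a responder.

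**2. Cross-type merge, subject level.** Uninjected 10 x 10 = 100 mm² and injected 20 x 20 = 400 mm² become one mass of 24 x 22 = 528 mm².
- Total: 528/500 = +5.6%.
- Uninjected burden: 100 to 0, -100%, a response.
- Injected burden: 400 to 528, +32%, which works against an injected response.
- General condition: an absorbed area *u* with other lesions of its type totalling *o*, unchanged, gives a reduction of *u*/(*u* + *o*). For *u* = 225 this is 100% (*o* = 0), 69% (*o* = 100), 50% (*o* = 225) and 43% (*o* = 300). A false response needs the absorbed lesion to be at least half of its type's burden.

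**3. Split, subject level.** A 600 mm² injected lesion splits into two equal parts with no tissue loss.
- Baseline plus new lesions, fragment classed as injected: 0% change.
- Baseline lesions only (Section 6), with other injected area *o*: reduction 300/(600 + *o*), that is 50% (*o* = 0), 33% (*o* = 300) and 25% (*o* = 600).
- If the fragment is classed as uninjected, its area is also added to the uninjected burden, which lowers the chance of an uninjected response.

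**4. Same-type merge.** For touching round lesions with d1 ≥ d2, measured as one mass, (d1 + d2) x d1 ≥ d1² + d2². Two 20 mm lesions go from 800 to 800 mm²; 20 mm and 15 mm go from 625 to 700. No false response arises.

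**5. Effect per subject.** One false responder adds 1/75 = 1.3 points if all 75 or so Arm 1 subjects are in the denominator. If only 15 to 30 have an evaluable uninjected burden (assumption), it adds 1/30 = 3.3 to 1/15 = 6.7 points. For scale, 15/75 = 20.0% (80% Clopper-Pearson CI 14.1 to 27.2) against 17/75 = 22.7% (16.4 to 30.1).

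**The case against.** The strongest reply is that protocol 6.2.1.1 makes these cases uncommon. It calls for all reasonably injectable lesions to be injected up to 4.0 mL per visit. By its Table 1 the two lesions in the merge example would take at most 0.5 + 1.0 = 1.5 mL, so both would normally be injected. The example needs a neighbour that is not injectable, or volume used up elsewhere. New injectable tumors also have first priority for injection, and injection at any time in the treatment period makes a lesion injected, so many fragments would return to the injected burden. This stands as an argument about frequency. It does not help a fragment first seen around week 12, which is also the last dosing visit, nor does it touch the lesion-level split or the Section 6 baseline-only wording.

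A reader might infer that the rules inflate response rates in one direction. The documents do not support that: the merge example raises injected burden by 32%, an uninjected fragment raises uninjected burden, and if the uninjected lesion is the larger one the false response falls on the injected side.

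A reader might also infer that uninjected response is this trial's evidence of a systemic effect. Protocol 2.3 links systemic effects to a lower distant metastasis rate, and 7.3.2 assigns the mechanism of systemic action to biopsies. The endpoint matters because it is a named secondary one, and no more should be claimed.

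**Conclusion.** The gap is real, and the stated 50% rule gives a wrong result in three definable situations: a split whose largest part is at most half the baseline area; a cross-type merge in which the absorbed lesion was at least half of its type's burden; and a split whose fragment falls outside the injected burden, when enough area leaves. The misattribution can raise or lower either rate. Neither document gives a merge or split frequency, so the 1.3 to 6.7 points above is an effect per subject and not an estimate of bias.

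The reach is limited to the lesion-level, injected/uninjected and lesion-subtype responses, which are Arm 1 only, secondary and descriptive. It is tempting to extend the point to overall modified WHO response. That does not follow: the largest index lesion stays measured after a merge, and measurable fragments are added to the sum. This rests on the whole merged mass being measured, as Appendix D appears to intend, and it excludes fragments too small to be measurable. RFS, R0 and pCR do not use these areas.

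**What to change.** In SAP 4.1.2.1.1 and Section 6:

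- **(a)** For lesion-level response, add the areas of all fragments back to the parent and do not count fragments as separate lesions. The example then reads 568/600, -5.3%.
- **(b)** In the subject-level burdens, give each fragment its parent's injection status and lesion type.
- **(c)** When lesions of different type merge, do not read the 0 x 0 mm entry as shrinkage. Keep the subject in the denominator and divide the merged area between the types in proportion to the pre-merge areas: 528 x 100/500 = 105.6 mm² uninjected and 528 x 400/500 = 422.4 mm² injected, each +5.6%. A simpler alternative is to count the subject as a non-responder for the absorbed type.
- **(d)** Make the Section 6 tumor burden definition agree with 4.1.2.1.1: baseline plus new measurable lesions.

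Simply extending the lesion-level stopping rule to subject level, or dropping the merged pair, would be a poor substitute for (c). With normally one scheduled assessment before surgery, the last one before the merge is baseline. Stopping there would make the subject non-evaluable and selectively remove those whose lesions grew together; dropping the pair does the same when no other lesion of that type remains.

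The cost is SAP wording and a little programming. The links between lesions are already collected under Appendix D, so no new data are needed. The affected rates may shift slightly in either direction. The overall modified WHO response should be left as it is.

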The baseline tumor burden for a subject is the sum of the initial area of baseline lesions of the specific lesion type.

- Tumor Burden

The tumor burden for a subject at a visit is the sum of the area at that visit of baseline lesions of the specific lesion type.

- Evaluable Tumor Burden

A subject is defined as having an evaluable tumor burden of a specific type (injected, uninjected) if they have at least one evaluable tumor burden assessment of the specific type. An evaluable assessment is one with a tumor burden that includes all lesions of the specific type with a non-missing area that were included in a baseline tumor burden assessment.

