## **7. Analysis Subsets**

### **7.1 Intent to Treat Analysis Set**

The primary analysis of all efficacy endpoints of the study will be conducted on the intent to treat analysis set defined as all randomized subjects who were randomized to either treatment arm. All subjects will be analyzed according to their treatment randomization.

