### **9.3 Handling of Missing and Incomplete Data**

#### **9.3.1 Efficacy**

The method for handling missing data is described in the definition for each of the efficacy endpoints ([Section 4](#)).

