**Table 2. Study Design Characteristics Example Endpoint Summary Table**

Endpoint	Primary Summary and Analysis Method	Sensitivity Analysis
Key Secondary Endpoints		

 
• Rate of R0 surgical resection;
 
• Rate of pCR
 
	
 
• 80% exact CI by randomized treatment arm in the ITT analysis set per Clopper-Pearson.
 
• 80% approximate exact CI for the between-arm difference per Wilson's score method with continuity correction.
 
	
 
• Repeat using the efficacy analysis set, if necessary.
 
• Multivariate logistic models may be used to explore the prognostic and/or predictive value of baseline factors.
 

Tumor response (Arm 1 Only): 
 
• Overall Tumor Response (per Investigator)
 
• Individual injected lesion response overall and by subtype (cutaneous / subcutaneous vs lymph node)
 
• Individual uninjected lesion response overall and by subtype (cutaneous / subcutaneous vs lymph node)
 
• Subject response on overall injected lesions
 
• Subject response on overall uninjected lesions
 
	
 
• For response rate use the Clopper-Pearson method to calculate exact 80% CIs;
 
• For time to response the Kaplan-Meier (K-M) estimate
 
• The tumor response analysis is performed in the ITT analysis set.
 
	
 
• Repeat using the efficacy analysis set, if necessary.
 

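### Subject-level injected and uninjected response uses an evaluable-only denominator that the SAP does not reconcile with its ITT rule, so the reported rate sits at or above the ITT rate

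*SAP*

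**What the plan says.** SAP 4.1.2.1.1 defines subject-level response, by injected or uninjected lesions, as a fall of at least 50% in the tumor burden of that type. It states that the incidence "will be reported as the proportion of subjects with an evaluable tumor burden of the corresponding type that achieves a response".

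SAP Section 6 defines the terms. A subject has an evaluable burden of a type "if they have at least one evaluable tumor burden assessment of the specific type". Completeness is required: "An evaluable assessment is one with a tumor burden that includes all lesions of the specific type with a non-missing area", referring to the lesions in the baseline burden. A lesion is evaluable if "it has an initial positive area followed by at least 1 assessment with a non-missing area". Injection status is set by what happens on treatment: "Baseline or new lesions that are reported as injected with talimogene laherparepvec at any time during the treatment period are considered injected lesions".

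SAP Table 2 lists subject response on injected lesions and on uninjected lesions in its tumor response row and adds: "The tumor response analysis is performed in the ITT analysis set". SAP 7.1 is general: "The primary analysis of all efficacy endpoints of the study will be conducted on the intent to treat analysis set", that is, all randomized subjects. Protocol 10.1.2 says the same, and protocol 10.1.1.2 defines these responses without any evaluability condition.

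On missing data, SAP 9.3.1 says only: "The method for handling missing data is described in the definition for each of the efficacy endpoints". Section 4 has no rule for a subject with no usable measurement on these endpoints. SAP Section 11, which lists departures from the protocol, does not mention the evaluable denominator.

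**The concern.** Two programmers working from the same SAP could produce different denominators: one following 4.1.2.1.1, the other following Table 2 and 7.1. If 4.1.2.1.1 is followed, randomized Arm 1 subjects without a complete later measurement disappear from the rate instead of counting as non-responders.

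That is easy to trigger. Protocol 7.2.2 schedules one on-treatment tumor assessment in Arm 1, at week 12 or shortly before surgery if treatment ends early. One missed visit, or one unmeasured lesion among several, can remove a subject. SAP 4.1.2.1.1 also closes subject-level response at the start of other anti-cancer therapy or at any lesion resection. A subject moved to either before a complete measurement is taken is therefore lost to the endpoint. SAP 3.1 lets the investigator make that move when growth or new tumors appear to warrant it.

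Response to neoadjuvant treatment has its primary analysis at the second interim (SAP 10.1) and may be supplied to regulators in ad hoc analyses (SAP 8.1), so the denominator needs to be unambiguous.

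**Working it through.** The plan states no response rate, evaluable count or sample size for this endpoint, so there is no figure of its own to reproduce.

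**Inputs from the documents.** About 150 subjects randomized 1:1 (SAP 3.1) gives N = 150/2 = 75 in Arm 1. Table 2 calls for exact 80% Clopper-Pearson intervals.

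**Assumed inputs, not in the documents.** The number of responders r, and the number of non-evaluable subjects m.

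**Formula.** With E = N − m evaluable subjects and the same r responders in both numerators:

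- ITT rate, non-evaluable counted as non-response: r/N
- SAP 4.1.2.1.1 rate: r/E = (r/N) × (N/E)

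N/E is at least 1, so the SAP rate is never lower. The two are equal if every subject is evaluable or if nobody responds.

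**Injected response, N = 75, assumed r = 25:**

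| m | E | Factor N/E | Rate | 80% CI |
|---|---|---|---|---|
| ITT | 75 | 1.00 | 25/75 = 33.3% | 26.1 to 41.3 |
| 4 | 71 | 1.06 | 25/71 = 35.2% | 27.6 to 43.4 |
| 8 | 67 | 1.12 | 25/67 = 37.3% | 29.4 to 45.8 |
| 15 | 60 | 1.25 | 25/60 = 41.7% | 33.0 to 50.8 |

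**Range over r.** Letting r run from 10 to 35, the excess over the ITT rate is 0.8 to 2.6 percentage points with m = 4, 1.6 to 5.6 with m = 8, and 3.3 to 11.7 with m = 15.

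**Uninjected response.** Suppose 30 Arm 1 subjects have uninjected lesions and 10 respond (again assumed). Keeping all 30 gives 10/30 = 33.3%. Dropping 5 as non-evaluable gives 10/25 = 40.0%. Dividing by every Arm 1 subject gives 10/75 = 13.3%, which counts people who have no lesion of that type and cannot respond. Literal ITT is therefore not the right denominator for this endpoint.

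**Never-dosed subjects.** Under Section 6 a lesion is injected only if an injection is reported. A randomized Arm 1 subject who is never dosed has no injected lesion and leaves the injected denominator; all of that subject's lesions become uninjected. A denominator restricted to subjects with a baseline lesion of the injected type would not bring the subject back, so the remedy has to name this group.

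**The case against.** The best defence is that Table 2's ITT line covers five endpoints, two of them individual-lesion rates whose units are lesions and one of them uninjected response. For those, ITT cannot mean every randomized subject in the denominator. It can be read as the source population, with 4.1.2.1.1 then giving the specific denominator openly and in advance. This stands in part: literal ITT does not fit uninjected response. It does not settle injected response, where an all-Arm-1 denominator is well defined. The SAP nowhere says that this is how the two statements fit together.

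Three stronger readings are tempting, and the documents do not support them.

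- A reader might infer that anyone who stops treatment before week 12 is dropped. Protocol 7.2.2 schedules imaging and response assessment within 2 weeks before surgery, and clinical measurement within 1 week before surgery, for exactly these subjects. Early stoppers who have that assessment stay in.
- A reader might infer that treatment failures are removed selectively and that the rate is therefore shown to be biased. One unmeasured lesion can equally remove a subject whose other lesions shrank. Counting the non-evaluable as non-responders is a conservative convention, and the rate is high only relative to it.
- A reader might infer that a common denominator would make these rates directly comparable with overall response. Overall response uses the modified WHO criteria, including nonindex lesions and progression through new lesions, whereas these endpoints use only a 50% reduction in burden.

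It is also fair to note that the Section 6 wording on an evaluable assessment does not itself say post-baseline. That is inferred from the evaluable-lesion definition and from response being a reduction from baseline.

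**Conclusion.** The point holds as an unreconciled conflict whose direction is known and whose size is not. Following 4.1.2.1.1, the subject-level injected and uninjected rates are at or above the rates that count non-evaluable subjects as non-responders, by the factor N/E. How far above depends on how many subjects lack a complete pre-surgery measurement, which the documents do not say. The percentages above rest wholly on assumed counts, and the excess is zero if everyone is evaluable.

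The conclusion also assumes that an evaluable assessment means a post-baseline one, and that non-response is the appropriate handling for an ITT response rate, which Table 2 does not spell out. The consequence is limited: the endpoints are secondary, descriptive and confined to Arm 1, with no between-arm comparison. RFS and the sample size are untouched.

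**What to change.** Replace the denominator sentence in SAP 4.1.2.1.1 and align Table 2 with it:

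- **Injected response:** all subjects randomized to Arm 1, including those never dosed.
- **Uninjected response:** dosed Arm 1 subjects with at least one baseline measurable lesion not reported as injected. State openly that this is not the full ITT set, and why.
- **Missing measurements:** count subjects without an evaluable post-baseline assessment as non-responders, say in Section 6 that the assessment must be post-baseline, and report how many subjects this affects for each endpoint.
- **Sensitivity analysis:** keep the evaluable-only rate, labelled as such.

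This takes a few sentences and no new data. The cost is that the headline rates become somewhat lower, since a responder whose measurement is incomplete counts as a failure. The labelled sensitivity analysis shows how much that matters.
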